2.2. Brief Background

Albiglutide has been approved in the European Union (EU), the US, and other countries for the treatment of T2DM as an adjunct to diet and exercise, as monotherapy (EU), or in combination with existing therapies. The efficacy and safety of albiglutide has undergone extensive testing both as monotherapy and in combination with oral anti-diabetic agents [Home, 2015]; [Ahren, 2014], [Weissman, 2014]; [Leiter, 2014]; [Nauck, 2015]. Reductions in HbA_{1c} are typically 0.3-1.0% with 30-mg uptitrated to 50-mg. In clinical trials, albiglutide demonstrated a GI side-effect profile similar to placebo [Ahren, 2014].

Exenatide is a 39 amino acid peptide. Due to its short half-life, exenatide is administered twice daily. The incidence of GI effects was reported most frequently at initiation of therapy (0-8 weeks) and decreased over time, i.e., nausea may resolve within 6-8 weeks in most patients [Heine, 2005]; [Meretto, 2008]; [Buse, 2004]; [DeFronzo, 2005]; [Kendall, 2005], [Zinman, 2007]; [Nauck, 2007]; [Barnett, 2007]. Exenatide has been approved in the US indicated as an adjunct to diet and exercise to improve glycemic control in adults with T2DM.

3. OBJECTIVE(S) AND ENDPOINT(S)

Objectives	Endpoints
Primary	

 To explore the effect of single dose 50 mg albiglutide compared to single dose 10 µg exenatide on regional brain activity and connectivity associated with nausea in healthy volunteers 	
 Resting-state BOLD signal (fMRI) Regional cerebral blood flow (rCBF) (fMRI-ASL) Glutamate concentration in nausea-associated brain regions (MRS) GABA concentration in nausea-associated brain regions (MRS)
Secondary	

 To evaluate autonomic effects of single dose 50 mg albiglutide compared to single dose 10 µg exenatide To assess safety and tolerability of single dose 50 mg albiglutide and single dose 10 µg exenatide 	
 Heart rate, heart rate variability, respiratory rate, ECG intervals, blood pressure, skin conductance level Vital signs, clinical laboratory tests, adverse events, Nausea ratings scale, GI VAS, and MSAQ
Exploratory	

 To evaluate gastric myoelectrical activity (GMA) of single dose 50 mg albiglutide compared to single dose 10 µg exenatide 	
 GMA: description of frequency region(s) (Bradygastria, Normal, Tachygastria)

4. STUDY DESIGN

4.1. Overall Design

This is a phase IV, 2-part, 2-period crossover, single dose, randomized, single blind (blinded to both the subject and the imaging evaluators analysing the MRI data), placebo- and active-controlled study in adult healthy volunteers who are susceptible to motion sickness. The study is designed to evaluate if albiglutide and exenatide modulate nausea-related brain activity and connectivity as assessed by MRI.

The two parts of the study, Part A and Part B are the same in design, both consisting of a screening stage, a dosing/assessment stage, and a follow-up visit. Part A will test the acquisition parameters and scanning paradigms to agree the experimental process for Part B. Data from Part A will inform progression, methods, and analysis plan for Part B. Placebo is used to enable albiglutide and exenatide to be dosed at different times relative to MRI due to differences in T_{max}, while preserving single-blind. Part A will initially randomize 4 subjects. Based on data review from the initial 4 subjects, an additional 4 subjects may be randomized for Part A. Reasons to enroll a second cohort include the need to modify acquisition parameters and scanning paradigms. If the modifications are substantial, a second cohort of 4 subjects will be added to Part A before progressing to Part B. Part B will randomize 20 subjects.

After screening, eligible subjects will be randomized to one of the four crossover dosing/imaging sequences. Each sequence includes three scanning visits: albiglutide plus scan, exenatide plus scan and an off-therapy –natural history scan with a 6-9 week

washout period between the dosing scans. Subjects will return for a follow-up visit post last dosing.

Note: Off-therapy MRI and post-dose MRI both include MRS, ASL, and resting state BOLD. In addition, the Off-therapy MRI will include a visual nauseogenic task fMRI (See Time and Events tables for full list of assessments during scan). *Number of subjects can be increased in Part A based on imaging evaluator judgment in consultation with the Investigator and the Sponsor after data review from 4 subjects.

In both Part A and Part B, subjects who meet the eligibility criteria will be randomized in a crossover fashion to one of 4 different sequences, each consisting of two dosing/imaging sessions (Session 1 and Session 2) separated by a 6-9-week washout period (Section 4.2 Table 1). Each subject will undergo a single off-therapy MRI during a separate Visit according to the randomization sequence to minimize the total number of scans per subject. The timing or sequencing of the off-therapy MRI will be randomized (i.e. Session 1 or Session 2) to account for potential learning effects. Each subject will undergo one off-therapy MRI, one post-dose albiglutide MRI and one post-dose exenatide MRI for a total of 3 MRI scans during the study. The visit schedule is set to allow the Off-therapy MRI scan visit to occur approximately 7 days prior to the post-dose scan within the Session as this is the minimal recommended time between scans. The visit on Day 5 allows the dosing of albiglutide or albiglutide placebo to occur 4 ± 1 days before the post-dose MRI i.e., at estimated T_{max} (3-5 days). Because of the short T_{max} (2 hrs) for exenatide, exenatide or saline placebo is given on the day of the MRI scan (Day 8). Therefore, MRI Session 1 and Session 2 each consist of 2 or 3 single-day out-patient visits according to the randomization schedule on the following days:

- Day 1 (Either Session 1 or 2 per randomization) for an off-therapy MRI scan consisting of resting-state fMRI, a nauseogenic task fMRI, ASL and MRS and nausea associated assessments,
- Day 5 for a single dose of 50 mg albiglutide or albiglutide placebo, and
- Day 8 for a single dose of 10 μ g exenatide or saline placebo followed by a post-dose MRI scan consisting of resting-state fMRI, ASL and MRS, and nausea associated assessments.

Subjects will be blindfolded when receiving the study medication injection to maintain the single-blind.

For all MRI sessions, subjects must fast overnight and will be instructed to refrain from eating and drinking anything but water starting at approximately 10 pm the night before or with in 8 hours of the start of their MRI appointment.

For the off-therapy session, MRI scan and nausea associated assessments will be conducted without prior injection (no drug, no placebo).

On post-dose scanning visits, subjects will be offered a meal after the procedure before leaving the unit, and capillary glycemia will be assessed.

The Investigator or medically qualified site staff will approve the release of the subject from the clinic or will provide treatment as per standard of care as required.

Subjects in either Part A or Part B will have a total of 8 planned visits: Screening, mock MRI, Session 1 or 2 off therapy MRI, Session 1 Day 5 dosing, Session 1 Day 8 dosing and post-dose MRI, Session 2 Day 5 dosing, Session 2 Day 8 dosing and post-dose MRI, and Follow-up (see Section 7.1 Time and Events table).

Part A data review

Safety data from each subject enrolled in Part A will be reviewed in stream by the study team, and imaging data will be pre-processed and assessed for quality in stream. Once the first 4 subjects enrolled in Part A have completed, data will be reviewed. The evaluation will include safety of exenatide and albiglutide administration at stated doses during MRI, fidelity of imaging and physiological (e.g. EGG) measures taken during the different MRI scan sessions. Outcome options may include modifying acquisition parameters and the scanning paradigm. If the modifications are substantial a second cohort of 4 subjects may be added to Part A before progressing to Part B. The decision to either modify the imaging paradigms, randomize 4 more subjects for Part A or progress to Part B will be made based on the imaging evaluator's judgment in consultation with the PI and Sponsor. A second interim data review will occur only if a decision to randomize 4 more for Part A is made after initial review of results from the first 4 subjects. This second review, should it occur, will use all data from 8 subjects. Adjustments to the study design of Part B (e.g., endpoint evaluation) may be made prior to progression to Part B.

Part A data review is part of the exploratory nature of this study and could result in refinement of endpoints and statistical analysis. These changes will be documented in the RAP and will not be considered an amendment to the Protocol.

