4.2. Treatment Arms and Duration

Table 1 Randomization Sequences for Part A and Part B

Sequence	Session 1 ^a			Session 2 ^a		
1	Off-therapy MRI	50 mg albiglutide	placebo ^c (post-dose MRI)		placebo ^b	10 µg exenatide (post-dose MRI)
2		50 mg albiglutide	placebo ^c (post-dose MRI)	Off-therapy MRI	placebo ^b	10 µg exenatide (post-dose MRI)
3	Off-therapy MRI	placebo ^b	10 µg exenatide (post-dose MRI)		50 mg albiglutide	placebo ^c (post-dose MRI)
4		placebo ^b	10 µg exenatide (post-dose MRI)	Off-therapy MRI	50 mg albiglutide	placebo ^c (post-dose MRI)

a. All administration will be given at fixed dose once daily by subcutaneous injection.

b. Placebo pen for albiglutide

c. Saline injection will be given as placebo for exenatide

All doses will be given in the morning. For all MRI sessions subjects must fast overnight and will be required to refrain from eating and drinking anything but water starting at approximately 10 pm the night before or within 8 hours of the start of their MRI appointment (see Section 6.10.1). It is recommended that the MRI scan be scheduled for early in the morning at the same time of day for each subject for all MRI Sessions.

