9.3. Data Analysis Considerations

There will be 4 fMRI and 3 MRS data points as shown in the table below:

Treatment Period ^a			Albiglutide	Exenatide
Day Relative to Period Start ^b	1 Off-therapy	1 Off-therapy	8 At T-max	8 At T-max
Visual Nauseogenic Task	No	Yes	No	No
MRI Data Point (DP)	DP1	DP2	DP3	DP4

Treatment Period ^a			Albiglutide	Exenatide
Resting State BOLD fMRI	✓		✓	✓
Nauseogenic task based BOLD fMRI		✓		
ASL	✓		✓	✓
MRS	✓		✓	✓

^a The order of the treatment periods will be randomized.

^b The day is relative to start of the Treatment Period.

For each subject, the Off-therapy Day 1 assessment(s) (DP1 and/or DP2 in table above) during the dosing/imaging sessions will serve as the baseline fMRI assessment.

Nauseogenic task BOLD signal (DP2,) will be assessed only during the off-therapy fMRI session. For the BOLD endpoint, the main contrasts of interest are the differences in the connectivity between albiglutide and off-therapy (DP3-DP2), between Exenatide and off-therapy (DP4-DP2), and between Albiglutide and Exenatide (DP3-DP4).

For resting state analysis rCBF ASL endpoints, the contrasts of interest are the differences DP3-DP1, DP4-DP1, and DP4-DP3. Similarly, for GABA and Glutamate concentrations, the main contrasts of interest are the differences DP3-DP1, DP4-DP1, and DP4-DP3.

The vection-induced nausea will provide a reference to regions of nausea associated brain activity. A group map will be calculated as in the previous Martinos Center study, and regions of interest (ROI) will be defined from the group map. These ROIs will then be used to perform masked comparison analyses for rCBF and MRS (where possible) data between the albiglutide vs exenatide and drug vs no-drug conditions. Such targeted analyses will allow for greater power than whole brain analyses which will need to be more stringently corrected for multiple comparisons.

There will be no imputation for missing data. Subjects who only partially complete the study may be included in some of the analyses where appropriate, depending on which data are available and which are missing.

Summary statistics (including number of subjects, mean, median, min, max, SD, SE) will be reported for continuous variables. The frequency and percentage will be used to summarize categorical variables.

Functional MRI Data

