9.4. Key Elements of Analysis Plan

Data from Parts A and B, as appropriate, will be pooled for final analysis. For comparisons between Albiglutide and exenatide, analysis of variance (ANOVA) will be used to analyze quantifiable endpoints with treatment and period as fixed effects, and subject as random effect. The contrast of interest for BOLD, ASL and MRS endpoints described in Section 9.3 will be tested using this model.

Pearson's and Spearman's correlation coefficients will be used to review relationships between selected quantifiable end points.

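### Does placing the off-therapy scan at random in Session 1 or 2 leave a scan-order bias in the drug-versus-off-therapy contrasts that the plan must adjust for?

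*Protocol*

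**What the plan says.** Protocol 4.1 gives each subject three scans: one off-therapy, one after albiglutide, one after exenatide. On the placement of the first it says "The timing or sequencing of the off-therapy MRI will be randomized (i.e. Session 1 or Session 2) to account for potential learning effects". Within its session the off-therapy visit comes "approximately 7 days prior to the post-dose scan within the Session", and there is a 6-9 week "washout period between the dosing scans". The four orders are set out in Section 4.2 under "Table 1 Randomization Sequences for Part A and Part B".

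For ASL, Section 9.3 says "the contrasts of interest are the differences DP3-DP1, DP4-DP1, and DP4-DP3", where DP1 is off-therapy, DP3 albiglutide and DP4 exenatide; the same three differences are listed for MRS. For BOLD the off-therapy task run (DP2) takes the place of DP1. Off-therapy thus enters two of the three contrasts for every modality. Section 9.4 specifies an ANOVA "with treatment and period as fixed effects, and subject as random effect" and adds: "The contrast of interest for BOLD, ASL and MRS endpoints described in Section 9.3 will be tested using this model".

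The SAP covers Part A only, because Part B was cancelled. SAP 2.1 says that group analysis of the 4 subjects will not be completed. SAP 11.1.1 nevertheless describes a paired t-test of off-therapy against exenatide for resting-state connectivity, and subject-level rCBF maps for off-therapy relative to exenatide. Neither document has a scan-order term.

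**The concern.** Learning or habituation depends on how many scans a subject has already had, not only on which session a scan falls in. The off-therapy scan always precedes dosing in its session, so it can never be the third scan. Protocol 4.1 offers the randomisation as the answer to learning effects and does not state this limit.

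If repeated scanning shifts the signal, part of that shift would be read as a drug effect in both drug-versus-off-therapy contrasts. Those contrasts are the only ones that address whether either drug changes brain activity relative to no drug. A period term does not help if period means session, and the paired t-test in SAP 11.1.1 adjusts for neither. The suggested remedy was a sensitivity model with scan number in place of session, together with a rule calling an effect robust only when both models agree.

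**Working it through.** **Inputs.** The orders come from Protocol Table 1 (O off-therapy, A albiglutide, E exenatide; the slash marks the washout). Equal allocation is assumed because no ratio is stated. Period is read as session, since Section 4.1 describes two periods and two sessions.

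| Sequence | Order | O is scan | A is scan | E is scan |
|---|---|---|---|---|
| 1 | O-A / E | 1 | 2 | 3 |
| 2 | A / O-E | 2 | 1 | 3 |
| 3 | O-E / A | 1 | 3 | 2 |
| 4 | E / O-A | 2 | 3 | 1 |
| Mean | | 1.50 | 2.25 | 2.25 |

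**Session.** Each condition falls twice in Session 1 and twice in Session 2, so session is balanced.

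**Scan order.** Let p1, p2, p3 be additive effects of being first, second or third. The drug mean carries (p1 + p2 + 2·p3)/4 and the off-therapy mean carries (p1 + p2)/2. Drug minus off-therapy is therefore biased by 0.5 × [p3 − (p1 + p2)/2].

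- Linear drift d per scan (0, d, 2d): 0.5 × (2d − 0.5d) = 0.75d.
- Effect g on the first scan only: −0.25g.
- A and E have identical position counts (1, 1, 2), so albiglutide minus exenatide has bias 0.
- Always scanning off-therapy first would give 2.5d − 1d = 1.5d, so the randomisation halves the linear bias.
- In calendar time off-therapy is on average only one week earlier than a drug scan, because each session is equally represented.

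A least-squares fit of this design gives the same 0.75d and −0.25g with and without a session term.

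**Scale.** The documents give no value for d. Assume 0.1 to 0.4 within-subject SD. At 24 subjects the standard error is √(2/24) = 0.289 SD, so the bias is 0.075/0.289 = 0.26 to 0.30/0.289 = 1.04 standard errors. A nominal 5% test would reject 5.7% to 17.4% of the time. At 4 subjects, one per sequence, the standard error is √(2/4) = 0.707 SD and the bias is 0.11 to 0.42 standard errors.

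**Scan number in place of session.**

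| Per unit of | Session model | Scan-number model |
|---|---|---|
| Linear drift per scan | 0.75 | 0 |
| First-scan effect | −0.25 | 0 |
| Session effect | 0 | −0.5 |
| Calendar drift per week, dosing scans 6 to 9 weeks apart | +1 | −2.0 to −3.5 |
| Standard error, 24 subjects | 0.289 SD | 0.323 SD |

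The standard error ratio is 0.323/0.289 = 1.12. With no session effect, the scan-number model has the lower mean squared error at 24 subjects only when d exceeds √(0.625/6 − 0.500/6)/0.75 = 0.144/0.75 = 0.19 SD. Fitting both terms removes both biases, but the standard error becomes 0.595 SD, about 2.1 times that of the planned model.

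**The case for a change.** The strongest case for a change is that Protocol 4.1 claims a safeguard that Table 1 only partly delivers, the planned model cannot repair it, and a sensitivity analysis costs one further model. The protocol deferred refinement of the analysis to the plan that would follow Part A, and the SAP that followed does not mention order.

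The arithmetic stands. Two of three contrasts per modality are exposed, and the mock scanner session in Protocol 7.2.3 may soften a first-scan effect but does not alter the imbalance over the three real scans.

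The remedy does not stand. The scan-number model exchanges sensitivity to repeated scanning for sensitivity to session and calendar drift, and nothing in the documents says which is larger. The two-model agreement rule lowers power from 81% to 70% for a true effect of 0.84 SD at 24 subjects. It also fails when the two disturbances oppose each other: with d = 0.4 and a session effect of −0.6, both models reject 11% of the time with no drug effect. It is a rule for single numbers and has no evident meaning for corrected whole-brain maps, in a study that sets no hypothesis (Protocol 9.1).

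The textual edits add little. Section 4.1 itself names session as the factor being randomised and says off-therapy precedes the post-dose scan. Table 1, repeated in SAP 2.3, shows every order. The planned listing of randomised and actual treatments (SAP 10.7.5, Listing 1) lets a reader recover each subject's planned scan order. Whether the paired t-test in SAP 11.1.1 will be run, given SAP 2.1, is a separate inconsistency.

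**Conclusion.** The observation is correct and no change to the plan follows. Scan order is balanced for the primary comparison and only partly for the off-therapy contrasts, with a bias of 0.75 of the per-scan step if the drift is linear. This is a fair trade-off: the off-therapy visit has to precede dosing within its session, and randomising its session halves the linear bias compared with always scanning it first.

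The alternative analysis is not clearly better, and changing Section 9.4 would alter no result because Part B was cancelled and group analysis was dropped. What remains is interpretive. The off-therapy versus exenatide comparisons in SAP 11.1.1 (the connectivity test if it is run, and the rCBF maps) are not adjusted for scan order. With one subject per sequence the exenatide-minus-off-therapy position differences are 2, 1, 1 and −1, mean 0.75, and the resulting bias is small against the noise for the range of d assumed here.

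These figures rest on equal allocation, additive order effects, period meaning session, and an assumed drift of 0.1 to 0.4 SD. If period meant the three scan occasions, the planned ANOVA would already remove additive order effects.

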4.2. Treatment Arms and Duration

Table 1 Randomization Sequences for Part A and Part B

Sequence	Session 1 ^a			Session 2 ^a		
1	Off-therapy MRI	50 mg albiglutide	placebo ^c (post-dose MRI)		placebo ^b	10 µg exenatide (post-dose MRI)
2		50 mg albiglutide	placebo ^c (post-dose MRI)	Off-therapy MRI	placebo ^b	10 µg exenatide (post-dose MRI)
3	Off-therapy MRI	placebo ^b	10 µg exenatide (post-dose MRI)		50 mg albiglutide	placebo ^c (post-dose MRI)
4		placebo ^b	10 µg exenatide (post-dose MRI)	Off-therapy MRI	50 mg albiglutide	placebo ^c (post-dose MRI)

a. All administration will be given at fixed dose once daily by subcutaneous injection.

b. Placebo pen for albiglutide

c. Saline injection will be given as placebo for exenatide

All doses will be given in the morning. For all MRI sessions subjects must fast overnight and will be required to refrain from eating and drinking anything but water starting at approximately 10 pm the night before or within 8 hours of the start of their MRI appointment (see Section 6.10.1). It is recommended that the MRI scan be scheduled for early in the morning at the same time of day for each subject for all MRI Sessions.

4.3. Type and Number of Subjects

This study will enrol both male and female healthy volunteers 18-50 years old who are right handed and sensitive to motion sickness. Approximately 60 healthy adults will be screened to achieve a total (from Parts A and B) of 24 or 28 randomized subjects.

In Part A, approximately 10 healthy adults will be screened to achieve 4 randomized. An additional 4 subjects (Cohort 2) may be randomized if changes to the acquisition parameters and scanning paradigm require confirmation before progressing to Part B.

If subjects prematurely discontinue the study or individual subject technical issues arise, subjects may be replaced at the discretion of the Investigator or imaging evaluators in consultation with the Sponsor. Subjects will be assigned to the same treatment sequence in order to meet the target number of subjects.

4.4. Design Justification

This exploratory study is designed to gain insight into a potential central mechanism of nausea associated with GLP-1R agonists and to determine if this mechanism can explain the clinically observed difference in GI tolerability between albiglutide and exenatide in clinical trials. Healthy volunteers will be enrolled in this study to allow an evaluation without the interference of morbidity. Single dose provides evidence of initial brain response to drug stimuli avoiding unnecessary exposure of healthy volunteers to the drugs being investigated. The crossover design is preferred because it allows the subject to act as their own control in the assessment of nausea which has a very strong subjective component [Levine, 2005]. Including subjects susceptible to motion sickness may

improve baseline nauseogenic central response. The assessment of CNS regional activation to nauseogenic drugs using fMRI comparing with standardized nauseogenic stimulus based on motion sickness is untested. Therefore, the study will be implemented in two parts. Part A will attempt to characterize brain activation with drug in comparison with brain activation with task identifying magnitude of signals, noise, artefacts, tolerability and safety. Data from Part A will be analyzed to identify adjustments needed to the imaging technique to progress to the main study, Part B.

fMRI is non-invasive and widely available modality to measure drug effects on brain function. [Wang, 2010; Duncan, 2014]. fMRI has been used to characterize nausea induced by perception of movement (motion sickness model). This study will combine the knowledge of pharmacological intervention and standardized task to study nausea, aiming to provide insight on drug effect in known patterns of brain activation and connectivity associated with nausea. Resting-state fMRI will measure BOLD signal to identify neuronal activity and relevant networks with and without study medication. fMRI imaging during visual nauseogenic task will assess the percent change in BOLD without study medication to identify the activation of brain regions associated with nausea. In addition to the hemodynamic changes as measured by BOLD signal and ASL, the study will investigate the correlation of chemical changes in two neurotransmitters, GABA and glutamate via MRS.

This exploratory study will include exenatide, a well-studied short-acting GLP-1 receptor agonist, as the active control. Exenatide has been shown to induce nausea at an incidence of 61.7% after a single 10 µg dose in healthy volunteers over 24 hrs post-dose [Ellero, 2010]. Temporal changes in the fMRI BOLD signal were observed after a single 5 µg dose of exenatide [McKie, 2013]. The timing of the MRI is chosen to coincide with albiglutide and active control expected Tmax. Therefore, the MRI is planned in 3 days for albiglutide but conducted after 1 hr for exenatide. The washout period between injections is 6-9 weeks due to the long half-life of albiglutide (T1/2= 5 days). Six to nine weeks will allow the scheduling of the scan visits to be aligned with the same phase of the menstrual cycle, when possible, for women of reproductive age.

This exploratory study includes placebo (albiglutide placebo or saline subcutaneous injection) to maintain the subject's blind and account for potential central activation that may result from receiving an injection prior to the MRI scan.

